8.2.9.2.3 Secondary and Exploratory Endpoints at the Interim Analysis

Secondary endpoints at the Interim Analysis

- 1) Percentage of subjects with Deep Response (DR) at Week 36 defined as either CR or VGPR at Week 36
- 2) Percentage of subjects with CR at Week 36
- 3) Ordinal response at Week 36 with the following five categories: CR, VGPR, MPR, SD, and PD determined by the investigator review

Exploratory endpoints at the Interim Analysis

- 1) Percentage of subjects with PR at Week 36
- 2) Best Overall Response (analyzed as an ordinal endpoint)
- 3) Best Percent Reduction in Tumor Line Length by Week 36
- 4) Percentage of subjects with sustained response at Week 36 -subjects who achieved response (confirmed CR or PR) prior to Week 36 but have not yet progressed at Week 36
- 5) Tumor growth kinetics endpoints: growth rate constant (GST) and time-to-growth (TTG)

Analysis of Secondary and Exploratory Endpoints

Binary secondary and exploratory endpoints will be compared between the two treatment groups by Fisher's exact test. All analyses will be performed at two-sided Type I error 0.05; there will be no control of Type I error across the primary and secondary hypotheses.

Summaries of the ordinal response (based on investigator review) distribution by week, including frequencies of categories and the mean response, will be provided.

A sensitivity analysis of the ordinal response at Week 36 based on the investigator review will be performed using the analysis described for the ordinal response at Week 36 based on central review.

Power of the Analyses of Secondary Endpoints at the Interim Analysis

If the true percentage of subjects with CR at Week 36 in (PBO+D+T) group is 10% (approximate expected percentage) and the true percentage of subjects with CR at Week 36 in (MK+D+T) group is 35%, the power for comparison of the percentages of subjects with CR at Week 36 is 71%. If the true percentage of subjects with DR at Week 36 in (PBO+D+T) group is 37.5% (approximate expected percentage) and the true percentage of

subjects with CR at Week 36 in (MK+D+T) group is 70%, the power for comparison of the percentages of subjects with CR at Week 36 is 79%.

If there are 4 subjects out of 40 (10%) with CR at Week 36 in the (PBO+D+T) treatment group, the (MK+D+T) treatment group should have at least 12 subjects with CR (36 %) at Week 36 for the comparison to be statistically significant. If there are 15 subjects with DR (37.5%) at Week 36 in the (PBO+D+T) treatment group, the (MK+D+T) treatment group should have at least 24 subjects with DR at Week 36 (60%) for the comparison to be statistically significant.

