8.2.9.2.1 Interim Decision Rules

If analysis of the ordinal response at Week 36 results in a statistically significant comparison in favor of the (MK+D+T) combination at one-sided Type I error of 0.025, the decision to

initiate Phase III study without waiting for PFS results will be considered. If the analysis shows that (MK+D+T) is worse than (PBO+D+T) at one-sided 0.05 Type I error, the futility will be established and the decision not to initiate a Phase III study may be considered.

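### Interim Deep Response example: 24/40 against 15/40 is not significant under the planned Fisher's exact test (p = 0.073); 25/40 is needed, and the CR figure of 12/40 is 30%, not 36%

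*Combined protocol and SAP*

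**What the plan says.** Section 8.2.9.2.3 fixes the test for the binary interim endpoints: "Binary secondary and exploratory endpoints will be compared between the two treatment groups by Fisher's exact test". It also fixes the level: "All analyses will be performed at two-sided Type I error 0.05", with no Type I error control across the primary and secondary hypotheses. Section 8.2.9.2.2 works with 40 subjects per arm, half of the first 80 randomized.

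The same section then gives power and boundary examples for the two secondary binary endpoints:

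- **CR at Week 36.** Power is 71% for 10% against 35%. With 4/40 CRs in the control arm, the (MK+D+T) arm "should have at least 12 subjects with CR (36 %) at Week 36" to reach significance.
- **DR (CR or VGPR) at Week 36.** Power is 79% for 37.5% against 70%. With 15 DRs (37.5%) in the control arm, the (MK+D+T) arm "should have at least 24 subjects with DR at Week 36 (60"%).

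The 79% sentence opens with the DR rate in the control arm and then changes endpoint: "subjects with CR at Week 36 in (MK+D+T) group is 70%, the power for comparison of the percentages of subjects with CR".

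**The concern.** A boundary count is a direct consequence of the test, the level and the arm sizes, all of which the plan states. The DR count does not follow from them. Read literally, the plan calls 24 against 15 significant in one paragraph, while the test it prescribes in another says otherwise.

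The CR figure is visibly inconsistent, because 12 out of 40 cannot be 36%. A reader cannot tell from the text alone whether the count or the percentage is the slip.

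DR is the first secondary endpoint listed for the interim, whose results go to the internal data monitoring committee. Section 8.2 says that no separate SAP will be issued, so this text is the only statistical record. At stake is the accuracy of that record and the reading of a borderline secondary result, not the interim decision itself.

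**Working it through.** **Inputs.** Fisher's exact test, two-sided 0.05 (Section 8.2.9.2.3). 40 per arm (Section 8.2.9.2.2). Control counts of 4/40 for CR and 15/40 for DR (Section 8.2.9.2.3).

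**Method.** With x responders on (MK+D+T) and c on control, condition on the total m = x + c. The number on (MK+D+T) is then hypergeometric:

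P(X = k) = C(40, k) × C(40, m − k) / C(80, m)

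The one-sided p-value is P(X ≥ x). With equal arms the distribution is symmetric, so the two-sided p-value is twice that.

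**Step 1: do the stated powers come from this test?** Summing the two binomials over all tables that Fisher's test declares significant in favour of (MK+D+T):

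| Comparison | Stated power | Exact Fisher | Normal approximation |
|---|---|---|---|
| 10% v 35% | 71% | 71.7% | 77.4% |
| 37.5% v 70% | 79% | 79.8% | 84.4% |

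The stated powers fit ordinary Fisher and not the normal approximation. The second row also supports reading the 79% sentence as a DR comparison, because 37.5% is the DR control rate in the boundary example and the CR comparison already has its own sentence.

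**Step 2: CR boundary against 4/40.**

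| (MK+D+T) CRs | Two-sided p |
|---|---|
| 11 | 0.0834 |
| 12 | 0.0482 |

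The count of 12 is reproduced. Its percentage is 12/40 = 30%. The printed 36% would need 0.36 × 40 = 14.4 subjects, which is not a whole number.

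**Step 3: DR boundary against 15/40.**

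| (MK+D+T) DRs | One-sided p | Two-sided p |
|---|---|---|
| 23 (57.5%) | 0.0583 | 0.1165 |
| 24 (60%) | 0.0365 | 0.0729 |
| 25 (62.5%) | 0.0218 | 0.0435 |

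For 24 against 15, m = 39 and P(X ≥ 24) = 0.0365, so two-sided p = 2 × 0.03645 = 0.0729. It also fails at one-sided 0.025. The first count to cross 0.05 is 25. A count of 24 would be significant against 14/40 (p = 0.0432), but the plan's 37.5% fixes the control count at 15.

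**Step 4: could another test explain 24?** Two-sided p-values, except where noted:

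| Test | CR 11 v 4 | CR 12 v 4 | DR 24 v 15 |
|---|---|---|---|
| Uncorrected chi-square | 0.0450 | 0.0253 | 0.0441 |
| Unpooled Wald | 0.0396 | 0.0209 | 0.0388 |
| Boschloo | 0.0473 | 0.0266 | 0.0495 |
| Fisher, one-sided at 0.05 | 0.0417 | 0.0241 | 0.0365 |
| Mid-p Fisher | 0.0516 | 0.0292 | 0.0488 |
| Barnard | 0.0846 | 0.0282 | 0.0478 |

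The first four would make 24 significant, but they would also lower the CR boundary to 11, against the stated 12. Mid-p Fisher and Barnard give both 12 and 24, but the plan names neither, and its powers match ordinary Fisher.

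**The case against.** The strongest reply accepts the arithmetic and disputes its weight.

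- **The sentence is an illustration, not a rule.** The Go and futility decisions in Section 8.2.9.2.1 turn on the ordinal response alone. The actual DR p-value would come from running Fisher's test, so an analyst following the plan would report 0.073 and not claim significance.
- **There is no Type I error control here to breach.** Neither the secondary interim comparisons nor the interim and final analyses together are adjusted (Sections 8.2.9.2.3 and 8.2.6).
- **The boundary is fragile.** It assumes an exact 40/40 split. If 24 of 39 on (MK+D+T) were compared with 15 of 41 on control, Fisher gives p = 0.0434.
- **It comes too late to matter.** Sections 5.2.5 and 7.1.5.3 report that the Part 3 final analysis is complete.
- **Another test may have been meant.** Mid-p Fisher or Barnard would yield both printed counts.

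The first four points stand and limit the consequence to the record. They do not make the sentence true: the example specifies its own counts and denominators, and with those 24 does not reach significance. The last point cannot be excluded from the documents, which do not show how 24 or 36% was obtained. But neither test is named, and the fit of the stated powers points to ordinary Fisher.

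**Conclusion.** The concern holds. With 40 per arm and Fisher's exact test at two-sided 0.05, the DR boundary against 15/40 is 25 (62.5%, p = 0.0435), not 24 (60%, p = 0.0729): an error of one subject. The CR count of 12 is right and its percentage should be 30%. The CR wording in the 79% power sentence is a slip for DR. Both power figures stand.

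This should be corrected because a stated significance threshold contradicts the plan's own test. The percentage and endpoint-label slips are clerical and would not merit a comment by themselves. Nothing in the interim decision rules, the PFS analysis or the sample size is touched. The conclusion rests only on inputs stated in the plan.

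**What to change.** In Section 8.2.9.2.3:

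1. In the DR example, change 24 to 25 and 60% to 62.5%.
2. In the CR example, change 36% to 30% and keep the count of 12.
3. In the 79% power sentence, replace CR with DR in both places.

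If the sponsor did intend a different test that gives 24, it should name that test and recompute the stated powers under it.

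The cost is a text edit. Section 8.2 calls for a protocol amendment only when primary or key secondary hypotheses, or their methods, change. None does here, so a note in the clinical study report would serve if the protocol is not otherwise being reissued.

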8.2.10 Compliance (Medication Adherence)

Drug accountability data for trial treatment will be collected during the study. Any deviation from protocol-directed administration will be reported.

8.2.11 Extent of Exposure

For a pembrolizumab regimen, a subject's extent of exposure to pembrolizumab (or matching IV placebo) is defined as the total number of doses of pembrolizumab (or matching IV placebo) the subject received. A subject's extent of exposure to dabrafenib or trametinib will be described through the cumulative dose of each drug.

Summary statistics will be provided to characterize Extent of Exposure, Time on Study Treatment (in months; calculated as the total number of days from the first post-randomization dose date to the date of the last dose of study medication multiplied by 12/365.24), and, for dabrafenib and trametinib, the Average Daily Dose. The summary statistics will be provided for the APaT population in Part 3, for each treatment group separately.

9.0 LABELING, PACKAGING, STORAGE AND RETURN OF CLINICAL SUPPLIES

9.1 Investigational Product

The investigator shall take responsibility for and shall take all steps to maintain appropriate records and ensure appropriate supply, storage, handling, distribution and usage of investigational product in accordance with the protocol and any applicable laws and regulations.

Clinical Supplies will be provided by the Sponsor as summarized in [Table 43](#).

Table 43 Product Descriptions

Product Name & Potency	Dosage Form
Pembrolizumab 100 mg / 4 mL	solution for IV infusion
Trametinib 2 mg	tablets
Trametinib 0.5 mg	tablets
Dabrafenib 75 mg	capsules
Dabrafenib 50 mg	capsules

9.2 Packaging and Labeling Information

Clinical supplies will be affixed with a clinical label in accordance with regulatory requirements.

Open label vials of pembrolizumab and open label bottles of trametinib and dabrafenib will be provided. No kitting is required.

9.3 Clinical Supplies Disclosure

Parts 1, 2, 4, and 5 of the trial is open-label; therefore, the subject, the trial site personnel, the Sponsor and/or designee are not blinded. Treatment identity (name, strength or potency) is included in the label text; random code/disclosure envelopes or lists are not provided.

Part 3 of the trial is blinded but provided open label; therefore, an unblinded pharmacist or qualified trial site personnel will be used to blind supplies. Treatment identity (name, strength or potency) is included in the label text; random code/disclosure envelopes or lists are provided.

At unblinding, trial personnel will dispense unblinded supplies. Additional details are included in the pharmacy and procedures manuals.

The emergency unblinding call center will use the randomization schedule for the trial to unblind subjects and to unmask treatment for Part 3 of this trial. In the event that the emergency unblinding call center is not available for a given site in this trial, the central electronic randomization system (IVRS/IWRS) should be used in order to unblind subjects and to unmask treatment/vaccine identity. The Sponsor will provide random code/disclosure envelopes or lists to the emergency unblinding call center.

Treatment identification information is to be unmasked ONLY if necessary for the welfare of the subject. Every effort should be made not to unblind.

In the event that unblinding has occurred, the circumstances around the unblinding (e.g., date and reason) must be documented promptly, and the Sponsor Clinical Monitor notified as soon as possible. Only the principal investigator or delegate and the respective subject's code should be unblinded. Trial site personnel and Sponsor personnel directly associated with the conduct of the trial should not be unblinded.

9.4 Storage and Handling Requirements

Clinical supplies must be stored in a secure, limited-access location under the storage conditions specified on the label.

Receipt and dispensing of trial medication must be recorded by an authorized person at the trial site.

Clinical supplies may not be used for any purpose other than that stated in the protocol.

9.5 Returns and Reconciliation

The investigator is responsible for keeping accurate records of the clinical supplies received from the Sponsor or designee, the amount dispensed to and returned by the subjects and the amount remaining at the conclusion of the trial.

For all trial sites, the local country Sponsor personnel or designee will provide appropriate documentation that must be completed for drug accountability and return.

9.6 Standard Policies

Trial site personnel will have access to a central electronic randomization system (IVRS/IWRS system) to allocate subjects, to assign treatment to subjects and to manage the distribution of clinical supplies. Each person accessing the IVRS system must be assigned an individual unique PIN. They must use only their assigned PIN to access the system, and they must not share their assigned PIN with anyone.

10.0 ADMINISTRATIVE AND REGULATORY DETAILS

10.1 Confidentiality

10.1.1 Confidentiality of Data

By signing this protocol, the investigator affirms to the Sponsor that information furnished to the investigator by the Sponsor will be maintained in confidence, and such information will be divulged to the institutional review board, ethics review committee (IRB/ERC) or similar or expert committee; affiliated institution and employees, only under an appropriate understanding of confidentiality with such board or committee, affiliated institution and employees. Data generated by this trial will be considered confidential by the investigator, except to the extent that it is included in a publication as provided in the Publications section of this protocol.

10.1.2 Confidentiality of Subject Records

By signing this protocol, the investigator agrees that the Sponsor (or Sponsor representative), IRB/ERC, or regulatory authority representatives may consult and/or copy trial documents in order to verify worksheet/case report form data. By signing the consent form, the subject agrees to this process. If trial documents will be photocopied during the process of verifying

worksheet/case report form information, the subject will be identified by unique code only; full names/initials will be masked prior to transmission to the Sponsor.

By signing this protocol, the investigator agrees to treat all subject data used and disclosed in connection with this trial in accordance with all applicable privacy laws, rules and regulations.

10.1.3 Confidentiality of Investigator Information

By signing this protocol, the investigator recognizes that certain personal identifying information with respect to the investigator, and all subinvestigators and trial site personnel, may be used and disclosed for trial management purposes, as part of a regulatory submissions, and as required by law. This information may include:

1. name, address, telephone number and e-mail address;
2. hospital or clinic address and telephone number;
3. curriculum vitae or other summary of qualifications and credentials; and
4. other professional documentation.

Consistent with the purposes described above, this information may be transmitted to the Sponsor, and subsidiaries, affiliates and agents of the Sponsor, in your country and other countries, including countries that do not have laws protecting such information. Additionally, the investigator's name and business contact information may be included when reporting certain serious adverse events to regulatory authorities or to other investigators. By signing this protocol, the investigator expressly consents to these uses and disclosures.

If this is a multicenter trial, in order to facilitate contact between investigators, the Sponsor may share an investigator's name and contact information with other participating investigators upon request.

10.1.4 Confidentiality of IRB/IEC Information

The Sponsor is required to record the name and address of each IRB/IEC member that reviews and approves this trial. The Sponsor is also required to document that each IRB/IEC meets regulatory and ICH GCP requirements by requesting and maintaining records of the names and qualifications of the IRB/IEC members and to make these records available for regulatory agency review upon request by those agencies.

10.2 Compliance with Financial Disclosure Requirements

Financial Disclosure requirements are outlined in the US Food and Drug Administration Regulations, Financial Disclosure by Clinical Investigators (21 CFR Part 54). It is the Sponsor's responsibility to determine, based on these regulations, whether a request for

Financial Disclosure information is required. It is the investigator's/subinvestigator's responsibility to comply with any such request.

The investigator/subinvestigator(s) agree, if requested by the Sponsor in accordance with 21 CFR Part 54, to provide his/her financial interests in and/or arrangements with the Sponsor to allow for the submission of complete and accurate certification and disclosure statements. The investigator/subinvestigator(s) further agree to provide this information on a Certification/Disclosure Form, commonly known as a financial disclosure form, provided by the Sponsor or through a secure password-protected electronic portal provided by the Sponsor. The investigator/subinvestigator(s) also consent to the transmission of this information to the Sponsor in the United States for these purposes. This may involve the transmission of information to countries that do not have laws protecting personal data.

10.3 Compliance with Law, Audit and Debarment

By signing this protocol, the investigator agrees to conduct the trial in an efficient and diligent manner and in conformance with this protocol; generally accepted standards of Good Clinical Practice (e.g., International Conference on Harmonization of Technical Requirements for Registration of Pharmaceuticals for Human Use Good Clinical Practice: Consolidated Guideline and other generally accepted standards of good clinical practice); and all applicable federal, state and local laws, rules and regulations relating to the conduct of the clinical trial.

The Code of Conduct, a collection of goals and considerations that govern the ethical and scientific conduct of clinical investigations sponsored by Merck, is provided in Section 12.1 - Merck Code of Conduct for Clinical Trials.

The investigator also agrees to allow monitoring, audits, IRB/ERC review and regulatory authority inspection of trial-related documents and procedures and provide for direct access to all trial-related source data and documents.

The investigator agrees not to seek reimbursement from subjects, their insurance providers or from government programs for procedures included as part of the trial reimbursed to the investigator by the Sponsor.

The investigator shall prepare and maintain complete and accurate trial documentation in compliance with Good Clinical Practice standards and applicable federal, state and local laws, rules and regulations; and, for each subject participating in the trial, provide all data, and, upon completion or termination of the clinical trial, submit any other reports to the Sponsor as required by this protocol or as otherwise required pursuant to any agreement with the Sponsor.

Trial documentation will be promptly and fully disclosed to the Sponsor by the investigator upon request and also shall be made available at the trial site upon request for inspection, copying, review and audit at reasonable times by representatives of the Sponsor or any regulatory authorities. The investigator agrees to promptly take any reasonable steps that are

requested by the Sponsor as a result of an audit to cure deficiencies in the trial documentation and worksheets/case report forms.

The investigator must maintain copies of all documentation and records relating to the conduct of the trial in compliance with all applicable legal and regulatory requirements. This documentation includes, but is not limited to, the protocol, worksheets/case report forms, advertising for subject participation, adverse event reports, subject source data, correspondence with regulatory authorities and IRBs/ERCs, consent forms, investigator's curricula vitae, monitor visit logs, laboratory reference ranges, laboratory certification or quality control procedures and laboratory director curriculum vitae. By signing this protocol, the investigator agrees that documentation shall be retained until at least 2 years after the last approval of a marketing application in an ICH region or until there are no pending or contemplated marketing applications in an ICH region or until at least 2 years have elapsed since the formal discontinuation of clinical development of the investigational product. Because the clinical development and marketing application process is variable, it is anticipated that the retention period can be up to 15 years or longer after protocol database lock. The Sponsor will determine the minimum retention period and notify the investigator when documents may be destroyed. The sponsor also recognizes that documents may need to be retained for a longer period if required by local regulatory requirements. All trial documents shall be made available if required by relevant regulatory authorities. The investigator must consult with and obtain written approval by the Sponsor prior to discarding trial and/or subject files.

ICH Good Clinical Practice guidelines recommend that the investigator inform the subject's primary physician about the subject's participation in the trial if the subject has a primary physician and if the subject agrees to the primary physician being informed.

The investigator will promptly inform the Sponsor of any regulatory authority inspection conducted for this trial.

Persons debarred from conducting or working on clinical trials by any court or regulatory authority will not be allowed to conduct or work on this Sponsor's trials. The investigator will immediately disclose in writing to the Sponsor if any person who is involved in conducting the trial is debarred or if any proceeding for debarment is pending or, to the best of the investigator's knowledge, threatened.

In the event the Sponsor prematurely terminates a particular trial site, the Sponsor will promptly notify that trial site's IRB/IEC.

According to European legislation, a Sponsor must designate an overall coordinating investigator for a multi-center trial (including multinational). When more than one trial site is open in an EU country, Merck, as the Sponsor, will designate, per country, a national principal coordinator (Protocol CI), responsible for coordinating the work of the principal investigators at the different trial sites in that Member State, according to national regulations. For a single-center trial, the Protocol CI is the principal investigator. In addition, the Sponsor must designate a principal or coordinating investigator to review the

trial report that summarizes the trial results and confirm that, to the best of his/her knowledge, the report accurately describes the conduct and results of the trial [Clinical Study Report (CSR) CI]. The Sponsor may consider one or more factors in the selection of the individual to serve as the Protocol CI and or CSR CI (e.g., availability of the CI during the anticipated review process, thorough understanding of clinical trial methods, appropriate enrollment of subject cohort, timely achievement of trial milestones). The Protocol CI must be a participating trial investigator.

